5.2 Concomitant Medications

In general, any concomitant medications should be avoided during the course of the study, unless it is required as a standard of care (necessary supportive care), prophylaxis or for the treatment of adverse event in the opinion of the treating investigator. The below recommendations should be followed, and concomitant medication should be clearly documented.

- Antimicrobial and/or anti-viral prophylaxis should be used according to local standard practice; Pneumocystis *jirovecii* pneumonia (PJP) and herpes zoster prophylaxis is strongly recommended. Similarly, chronic carriers of HBV should receive prophylactic anti-viral therapy.
- Hematopoietic growth factors (e.g., erythropoietin, GM-CSF and G-CSF) can be used for the management of acute toxicities such as febrile neutropenia when clinically indicated or at the discretion of the investigator.
- Prophylactic anti-emetic treatment is discouraged at the start of study treatment; however, patients can receive appropriate anti-emetic treatment at the first onset of

CONFIDENTIAL Page 30 of 66

nausea or vomiting and as required thereafter, in accordance with local standard practice.

- Transfusions may be given, based on standard criteria and clinical judgment.
- Corticosteroids are allowed for the symptomatic control of brain metastases provided the dose is stable before and during the study and they are started at least 4 weeks prior to the start of study treatment.
- Bisphosphonates (e.g., zoledronic acid and pamidronate) and monoclonal antibody denosumab are allowed for bone metastases/bone pain.
- Concurrent palliative radiotherapy for pain relief is allowed at the site of bone metastases that were present at baseline, provided the investigator does not feel that these are indicative of clinical disease progression during the study period; and radiotherapy is limited to an area other than the sole site of measurable or evaluable disease. Study treatment should be discontinued for a minimum of 3 days before a patient undergoes palliative radiation.
- If concomitant treatment of drugs metabolized by CYP3A4/CYP2C9 enzymes are clinically warranted, careful observation of the patient is advised.
- Low molecular weight heparin (LMWH) and Direct Oral Anticoagulant (DOA) such as dabigatran and edoxaban are acceptable for prophylaxis and/or treatment of venous thrombosis. Careful observation of the patient is advised while using apixaban and rivaroxaban.

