5.3 Prohibited Medications

The following treatments are prohibited while on clinical trial:

- Any other anti-cancer therapy (e.g., radiation therapy, hormonal, immunotherapy or biologic therapy).
- Strong inhibitors or inducers of CYP3A4. Patients should stop using these medications at least 48 hrs or 5 half-lives (whichever is shorter) prior to C1D1.
- Strong inhibitors or inducers of CYP2C9. Patients should stop using these medications at least 48 hrs or 5 half-lives (whichever is shorter) prior to C1D1.
- Substrates of CYP3A4 enzyme with a narrow therapeutic range. Patients should stop using these medications at least 48 hrs or 5 half-lives (whichever is shorter) prior to C1D1.
- Use of heparin and warfarin for prophylaxis and/or treatment of venous thrombosis is prohibited. These drugs should be stopped at least 48 hrs prior to C1D1.
- Herbal or alternative medicines are not allowed throughout the trial. Patients should stop using these medications at least 48 hrs prior to C1D1.
- Live attenuated vaccine (e.g., Flu vaccine, pneumovax, varicella) should not be administered whilst the patient is receiving study medication.
- Concurrent medications or substances with the potential to affect the activity of tenalisib as reviewed and confirmed by medical monitor.
- Any other investigational agent.

CONFIDENTIAL Page 31 of 66

Decision on discontinuation of the patient who received concomitant/prohibited medication will be taken by the PI in consultation with Medical Monitor on a case-to-case basis, after reviewing ongoing clinical benefit and risk. The decision to allow a patient to continue will be documented and archived at the site and at Rhizen.

5.4 Procedures for Monitoring Patient Compliance.

The following measures will be employed to ensure treatment compliance.

- The study staff will instruct patients to bring any unused study drug to the site.
- The study staff/designee will count and record the number of used and unused study drug tablets.
- The study coordinator will confirm adherence to the dosing regimen with the patient.
- He/she will record the number of tablets returned, the date returned and determine treatment compliance before dispensing new medication to the study patient.
- Compliance below 80% will require counseling of the patient by study site personnel.

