8 ASSESSMENT OF EFFICACY

8.1 Specification of the Efficacy Parameters

Initial disease assessment of patients should be performed within 28 days prior to the first dose of study drug using computed tomography (CT) and/or magnetic resonance imaging (MRI). This scan will be considered as baseline scan. The PI should review baseline scan images to confirm the subject has measurable disease as defined in the inclusion criteria. Scan performed as part of routine clinical management is acceptable for use as the baseline scan if it is of diagnostic quality and performed within 28 days prior to the C1D1, or as approved by the medical monitor if it is out of window period.

Subsequent scan (CT and/or MRI as applicable) should be done at C3D1 (± 7 days) and approximately 8 weeks thereafter (± 7 days), and/ or at the EOT and so on or as clinically indicated (if clinical progression is suspected). If a CR or PR is noted, confirmatory scans should be performed at least 4 weeks after the initial response was first documented. The scan should be reviewed by site investigator/radiologist/designee and tumour response will be assessed according to the revised Response Evaluation Criteria in Solid Tumour guideline (RECIST) version 1.1.[21]

8.2 Images included in the assessment.

A CT with IV contrast will be the primary modality for assessment, unless the patient has an allergy to contrast that cannot be controlled with pre-medications. If patients are unable to receive iodinated CT contrast, the preferred imaging is non-contrast CT of the chest, and MRI of the abdomen and pelvis with contrast. Tumour imaging should remain consistent throughout study and should include those thought by investigator to best capture status of disease. For skin nodules, CT or MRI will be the preferred modality of assessment. Digital photography will not be acceptable as a method of assessment for skin lesions.

8.3 Measurable and non-measurable disease:

Eligibility of lesions for quantitative assessment will be determined at baseline, with target lesions selected from the measurable lesions identified. After baseline, target lesions will always be assessed quantitatively, and non-target lesions will be assessed qualitatively, with no further evaluation of measurability according to these definitions.

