8.3.1 Measurable Disease

A lesion is considered measurable, if it meets one of the measurability criteria described above.

CONFIDENTIAL Page 50 of 66

- A lesion is considered measurable if it has a diameter of ≥ 10 mm in the axial plane on CT or MRI, assuming that the slice thickness is 5 mm or less. If the slice thickness is greater than 5 mm, the minimum size increases to two times the slice thickness.
- Pathological lymph nodes are considered measurable if the short axis (greatest dimension perpendicular to the longest diameter) is ≥ 15 mm at baseline.
- Skin nodules will be considered measurable lesion if they are assessed on CT or MRI.
 Digital photography will not be acceptable as a method of assessment for skin lesions.
 Discrete skin nodules that are not visible on CT or MRI should be considered non-measurable lesions.
- Bone lesions that are lytic or mixed lytic-blastic, which have soft tissue components seen on CT or MRI, and which meet size criteria above, may be measurable.
- Cystic metastases may be considered measurable, but solid lesions are preferred for selection as target.

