8.3.2 Non-Measurable Disease

A lesion is considered non-measurable, if it does not meet the measurability criteria described above. Example of non-measurable lesion included.

- A lymph node that has a short axis diameter of 10-14 mm is considered evaluable, but not measurable. Nodes with a short axis diameter of < 10 mm are considered normal.
- Palpable skin nodules that are not discernible using CT or MRI are considered evaluable but not measurable for this study.
- Bone lesions that are blastic are non-measurable.
- Simple cysts are considered benign by default.
- Malignant ascites or pleural/pericardial effusions, lymphangitic infiltration of skin or lung, leptomeningeal disease, inflammatory breast disease, and infiltrative disease without clear borders.
- Lesions seen on bone scan, or modalities other than CT or MRI (plain X-ray [with the exception for lung lesions], PET etc.) cannot be measured. These modalities can be used only to determine whether a lesion is present or absent.
- Previous local treatment: A previously irradiated lesion (or lesion subjected to other local treatment) is non-measurable unless it has progressed since completion of previous treatment.

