8.4 Baseline Lesion Selection and Documentation

Target lesions will be chosen from among the measurable lesions. The lesions chosen should be the largest, most reproducible, and most representative of the overall disease distribution.

- Target lesions: All measurable lesions up to a maximum of 5 lesions total, and 2 lesions per organ, should be selected as target lesions. Paired organs (lungs, kidneys, adrenals, ovaries) are considered one organ. The lymph nodes collectively are considered one organ.
- **Non-nodal target lesions** are measured in the longest diameter in the axial plane (on CT or MR). Malignant lymph nodes are always measured in the short axis diameter (greatest dimension perpendicular to the longest diameter). The appropriate measurements for all

CONFIDENTIAL Page 51 of 66

target lesions chosen at baseline will be added to produce the recorded sum of diameters, which will be recorded.

• Other disease present at baseline should be recorded as 'Non-target lesions'.

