8.5 Assessment of Response

The overall response for each visit is a combination of target lesion response, non-target lesion response, and the presence or absence of new lesions. **Target lesions measurements** should be performed in the same manner as at baseline. The sum of diameters of all target lesions must be calculated and compared to the baseline value and to the nadir value (the smallest value previously seen during the trial, which may be the same as baseline). The following special rules apply to lesion measurements:

- If two target lesions coalesce the longest diameter measurement of the coalesced mass is used. If a large target lesion splits, the longest diameter of each fragment is measured, and the sum is used.
- Measurements for target lesions that become small should continue to be recorded, as long as the investigator is confident in the accuracy. If a target lesion is considered to have completely disappeared, 0 mm should be recorded. If it is too small to measure accurately, but is still present, a default value of 5 mm should be recorded.
- When nodal lesions decrease to < 10 mm (normal), the actual measurement should still be recorded.

Target lesion response categories are defined as follows:

- Complete response (CR): Disappearance of all non-nodal target lesions. Target lymph nodes must reduce to < 10 mm in short axis.
- Partial response (PR): At least a 30% decrease in the sum of diameters of target lesions, compared to the sum at baseline.
- Progressive disease (PD): At least a 20% increase in the sum of target lesion measurements, compared to the smallest sum on study (including baseline). Also, the absolute increase in the sum has to be at least 5 mm.
- Stable disease (SD): If none of the above criteria meets.

Non-target lesion response assessment is qualitative. Categories are defined as follows:

- CR: Disappearance of all non-nodal non-target lesions. Non-target lymph nodes must reduce to < 10 mm in short axis. Note: If tumour markers are initially above the upper normal limit, they must normalize for a patient to be considered in complete clinical response.
- PD: Unequivocal progression of non-target lesions, evaluated as a whole, such that it is clear that treatment has failed, and disease is progressing, regardless of the status of the target lesions.
- Non-CR/Non-PD: Neither CR nor PD criteria are met.

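### A bone target lesion irradiated on study stays in the sum of diameters, so radiation shrinkage can be scored as a PR and can shift PD in either direction

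*Protocol*

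**What the plan says.** Protocol section 5.2: "Concurrent palliative radiotherapy for pain relief is allowed at the site of bone metastases that were present at baseline". Two conditions follow. The investigator must not regard the sites as clinical progression, and "radiotherapy is limited to an area other than the sole site of measurable or evaluable disease". Target lesions as such are not excluded from the field.

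Protocol section 5.3 lists as prohibited "Any other anti-cancer therapy (e.g., radiation therapy, hormonal, immunotherapy or biologic therapy". It does not refer back to the allowance in 5.2.

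On lesion selection, section 8.3.1 says that "Bone lesions that are lytic or mixed lytic-blastic, which have soft tissue components seen on CT or MRI" may be measurable if they meet the size criteria. Section 8.4 adds: "All measurable lesions up to a maximum of 5 lesions total, and 2 lesions per organ, should be selected as target lesions".

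After baseline, section 8.3 has target lesions always measured, "with no further evaluation of measurability according to these definitions". Section 8.5 requires: "The sum of diameters of all target lesions must be calculated and compared to the baseline value", and to the nadir.

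The one rule on irradiated lesions is in section 8.3.2: a lesion that has already had local treatment "is non-measurable unless it has progressed since completion of previous treatment".

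Table 9 of the protocol allows a not-evaluable entry for non-target lesions only. SAP sections 6.4.2 and 8.7.2 have no provision for radiotherapy given on study: no exclusion, no censoring and no sensitivity analysis.

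**The concern.** Section 8.3.2 accepts that local treatment undermines a lesion as a measure of drug effect. That protection stops at baseline, because measurability is not revisited afterwards. A bone target treated for pain during the study is then measured, summed and compared with thresholds as if tenalisib were the only influence on it.

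Visit response feeds ORR, CBR, DoR, PFS and the percentage without progression at 6 months. The trial is open label, response is read by the investigator, and there are 20 patients per arm with no untreated arm. A response produced by radiation would be credited to the dose in an arm where each patient counts heavily. Section 1.5.2 gives the purpose as choosing between the two doses.

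**Working it through.** The plan states no figure on this point, so there is nothing to reproduce. The check is RECIST arithmetic under the rules of section 8.5. **All lesion sizes below are assumptions; the documents give none.**

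Notation:
- w = irradiated lesion's share of the baseline sum
- s = its fractional shrinkage
- g = fractional growth of the other targets taken together
- change in sum = -w·s + (1 - w)·g

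**1. PR from the irradiated lesion alone (g = 0).** Section 8.5 needs a fall of at least 30%, so w·s ≥ 0.30. The shrinkage required, 0.30/w, is:
- w = 0.3: 100%
- w = 0.4: 75%
- w = 0.5: 60%
- w = 0.6: 50%
- w = 0.7: 43%

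Below w = 0.3 a PR from this lesion alone is impossible.

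Example: bone 45 mm + other 20 mm = 65 mm. Bone falls to 25 mm and the other is unchanged: sum 45 mm, 45/65 - 1 = -30.8%, scored PR. Check: w = 45/65 = 0.692, s = 20/45 = 0.444, product 0.308. Without the irradiated lesion the change is 0%, which is SD.

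The confirmatory scan at 4 weeks or later (section 8.1) does not help, because it cannot separate radiation shrinkage from drug effect.

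**2. PD masked: shrinkage and growth in the same scan interval.** Section 8.5 needs the sum to rise at least 20% and 5 mm over nadir. With baseline as nadir, g must reach (0.20 + w·s)/(1 - w):
- w = 0.5: 40% at s = 0, 70% at s = 0.3, 90% at s = 0.5
- w = 0.3: 29%, 41% and 50% at the same values of s

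Example: bone 40 mm + other 40 mm = 80 mm, and the other target grows to 60 mm (g = 50%).
- Bone unchanged: 100/80 - 1 = +25%, +20 mm, PD.
- Bone at 28 mm after radiation (s = 0.3): 88/80 - 1 = +10%, SD.

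**3. PD brought forward: shrinkage recorded first.** Return to 45+20 mm, with a scan after radiation at 25+20 = 45 mm. That becomes the nadir.
- With radiation: PD at 1.2 × 45 = 54 mm, so the other target need reach only 54 - 25 = 29 mm.
- Without radiation (bone stays 45 mm): PD at 1.2 × 65 = 78 mm, so the other target must reach 78 - 45 = 33 mm.

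**4. Size per patient.** 1/20 = 5 percentage points. With exact 95% limits, as in SAP section 8.7, 4/20 is 20% (5.7% to 43.7%) and 5/20 is 25% (8.7% to 49.1%).

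**The case against.** The case against is substantial in four respects.

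- **Several conditions must coincide.** There must be a bone lesion with a measurable soft-tissue component, disease at another site, and painful disease irradiated but not judged progressive. For a PR from that lesion alone, it must also make up at least 30% of the baseline sum. The documents do not allow the frequency to be estimated. This stands, and it limits the weight of the point.
- **The sum is not the only route to PD.** New lesions and unequivocal non-target progression each give PD under section 8.5 and Table 9. PFS also counts deaths. Only target-sum PD can be hidden. This stands.
- **A reader might infer that every affected patient is biased towards activity.** The documents do not support that. PD is measured from the smallest sum on study, so step 3 shows it called earlier.
- **A reader might also treat any unirradiated target that grows 20% and 5 mm as hidden PD.** Section 8.5 applies that rule to the sum. Take 45+20 mm with the second lesion growing to 28 mm (+40%, +8 mm). Without radiation the sum is 73 mm, 73/65 - 1 = +12.3%, already SD. With bone at 30 mm it is 58 mm, 58/65 - 1 = -10.8%, again SD. Radiation hides nothing there; masking needs sizes such as those in step 2.

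On sections 5.2 and 5.3, it can be argued that a specific allowance for pain relief overrides a general prohibition. That may be what was meant, but neither section says so. A site could record the same event as permitted or as a deviation, and a deviation classed as major removes the patient from the PP population.

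**Conclusion.** The gap is real. Followed as written, the rules can score radiation shrinkage as a PR, and nothing in Table 9 or the SAP corrects it.

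- **ORR and CBR:** the bias is upward. For CBR it matters when the patient would not otherwise have SD of at least 24 weeks. The false responder also enters the DoR analysis.
- **PFS and the 6-month endpoint:** distortion can run either way, depending on whether shrinkage is recorded with the growth or before it.

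The size is 5 percentage points per affected patient in an arm of 20. The number of such patients is unknown, and the worked examples rest on assumed diameters. What does not depend on them is the condition w·s ≥ 0.30 for a PR with the other targets unchanged. The separate mismatch between sections 5.2 and 5.3 on radiation also needs to be reconciled.

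**What to change.** - **Response rule.** In protocol section 8.5 and SAP section 6.4.2, state that from the radiotherapy date a target lesion irradiated on study cannot contribute to a new CR or PR, while a response documented before radiotherapy stands. Say also what visit response is recorded when a response is blocked this way, since Table 9 has no row for a target that cannot be evaluated.
- **Sensitivity analysis.** Repeat the primary endpoint, ORR, CBR and PFS with irradiated targets removed from the baseline, nadir and visit sums alike. This addresses the two-way effect on PD without choosing one re-based PD rule for the main analysis.
- **Data.** Flag these patients in the target-lesion listing (16.2.6.2), which already shows individual diameters. Confirm that the anatomical site of on-study radiotherapy is captured. It might be assumed that it is, but the site column is in the prior-therapy listing (16.2.4.3). The listing for concomitant non-drug treatments (16.2.4.6) shows dates and a comment but no site.
- **Consistency.** Reconcile sections 5.2 and 5.3 on radiation. No view is offered on what the clinical rule should be.

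The cost is wording in two documents and one small extra analysis. An occasional patient will lose a PR. SAP section 5.1 records that the study was closed early, so a protocol edit cannot change data already collected; the SAP rule and the sensitivity analysis are the parts that can still act on the results.

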5.3 Prohibited Medications

The following treatments are prohibited while on clinical trial:

- Any other anti-cancer therapy (e.g., radiation therapy, hormonal, immunotherapy or biologic therapy).
- Strong inhibitors or inducers of CYP3A4. Patients should stop using these medications at least 48 hrs or 5 half-lives (whichever is shorter) prior to C1D1.
- Strong inhibitors or inducers of CYP2C9. Patients should stop using these medications at least 48 hrs or 5 half-lives (whichever is shorter) prior to C1D1.
- Substrates of CYP3A4 enzyme with a narrow therapeutic range. Patients should stop using these medications at least 48 hrs or 5 half-lives (whichever is shorter) prior to C1D1.
- Use of heparin and warfarin for prophylaxis and/or treatment of venous thrombosis is prohibited. These drugs should be stopped at least 48 hrs prior to C1D1.
- Herbal or alternative medicines are not allowed throughout the trial. Patients should stop using these medications at least 48 hrs prior to C1D1.
- Live attenuated vaccine (e.g., Flu vaccine, pneumovax, varicella) should not be administered whilst the patient is receiving study medication.
- Concurrent medications or substances with the potential to affect the activity of tenalisib as reviewed and confirmed by medical monitor.
- Any other investigational agent.

CONFIDENTIAL Page 31 of 66

Decision on discontinuation of the patient who received concomitant/prohibited medication will be taken by the PI in consultation with Medical Monitor on a case-to-case basis, after reviewing ongoing clinical benefit and risk. The decision to allow a patient to continue will be documented and archived at the site and at Rhizen.

5.4 Procedures for Monitoring Patient Compliance.

The following measures will be employed to ensure treatment compliance.

- The study staff will instruct patients to bring any unused study drug to the site.
- The study staff/designee will count and record the number of used and unused study drug tablets.
- The study coordinator will confirm adherence to the dosing regimen with the patient.
- He/she will record the number of tablets returned, the date returned and determine treatment compliance before dispensing new medication to the study patient.
- Compliance below 80% will require counseling of the patient by study site personnel.

6 TRIAL ASSESSMENT AND PROCEDURE

6.1 Overview

The Schedule of Event summarizes the trial procedures to be performed at each visit and is divided into following:

- 1. Screening (Day -28 to Day 0)
- 2. On treatment procedures (C1D1 to EOT)
- 3. End of Treatment (within 7 days from the last dose)
- 4. End of Study (Day +30 from the last dose)

Individual trial procedures are described in detail below. It may be necessary to perform these procedures at unscheduled time points if deemed clinically necessary by the investigator. Multiple procedures may be scheduled at the same time point relative to tenalisib.

